9.4.4 BASELINE DESCRIPTIVE STATISTICS

Categorical data collected at baseline will be presented as percentages. Continuous data will be presented as means with standard deviations. Because we are using cluster randomization with a relatively small number of randomization units, t-tests and chi-squares will be used to test for group differences at baseline.

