9.2 SAMPLE SIZE DETERMINATION

Power Analysis For Pre-Post Trial – Under the assumption of 24 clinics, at least 500 eligible MHS patients in each clinic in each six-month period, a rate of documented OUD of 1% pre-screening, a conservative estimate of 0 correlation between pre- and post-percentages, and an alpha significance level of 0.05, we will have 80% power to detect an increase from a pre-screening percentage of 1% to a post-period percentage of 1.7%.

Power Analysis For Effectiveness Trial - Assuming a coefficient of variation of 0.33 for the continuous outcome of days of illicit opioid use⁶⁷⁶ and SF12V MCS scores⁶⁶⁸⁷, a highly conservative intraclass correlation within clinics of 0.03, 12 clinics per group and 40 patients per clinic (n=960, accounting for NIH Behavioral and Social Intervention Clinical Trial Protocol Template v3.0 - 20180827

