20% attrition), we will have 80% power to detect an effect size of 0.31. We chose to use a highly conservative intraclass correlation to ensure sufficient power for secondary outcomes and mediation analyses (Hypothesis 2b). Thus, conservatively we will have 80% power to detect a 10 % difference in number of days using illegal opioids in the past month (e.g., 15.00 days compared to 13.5 days) and 10% difference in MCS scores (e.g., 40 compared to 36) between CHAMP and CoCM for MHS only clinics. Because these are multiple primary outcomes (and not co-primary outcomes), this power analysis assumes a Bonferroni correction for the two multiple primary outcomes. Specifically, the intervention will be interpreted to have been successful if there is a significance group different between either primary outcome, not both primary outcomes. Because of recruitment challenges, power analyses are also now provided for the lower bounds of expected enrollment. The lower-bounds power analysis assumes that we will recruit 360 study participants instead of 1200. For this lower-bounds power analysis, we assume a more realistic intraclass correlation of 0.01 instead of 0.03. Collaborative care trials conducted by [name] (MPI) and [name] (NIMH collaborator) found intraclass correlation coefficients in the range of 0.008-0.001).^{30,66} Assuming a coefficient of variation of 0.33 for the continuous outcome of days of illicit opioid use⁶⁷ and SF12V MCS scores⁶⁸, an intraclass correlation within clinics of 0.01, 12 clinics per group, 15 patients enrolled per clinic (n=288 accounting for 20% attrition), we will have 80% power to detect an effect size of 0.41. The sample size of 360 does not represent a revised enrollment target, and we will continue to enroll as many study participants as possible (up to 1,200) using enhanced recruitment methods and by extending the recruitment period if possible.

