9.4 STATISTICAL ANALYSES

9.4.1 GENERAL APPROACH

Statistical Analysis Plan - There will be a formal Statistical Analysis Plan that will be completed prior to unblinding of the Effectiveness trial data. The statistical plan will be posted publicly or registered before the study begins.

Reporting of Descriptive Statistics – Categorical data collected at baseline will be presented as percentages. Continuous data will be presented as means with standard deviations.

Statistical Tests – An alpha level of 0.05 and two-tailed tests will be used to determine statistical significance.

Covariates – Covariates will be included if they are theoretically related to both the dependent variable and the probability of having missing data, and will be specified later in the SAP.

Test of Distributional Assumptions – We will examine residuals for normality. If residuals are not approximately normally distributed, we will use a sandwich estimator (e.g., robust maximum likelihood estimator) to correct standard errors. Note that the treatment effect is a binary indicator and consequently, the point estimate for treatment condition will be unbiased, conditional on other model effects being specified correctly. For continuous covariates, we will examine scatterplots and partial regression plots to ensure the linearity assumption is reasonable. If linearity appears to be meaningfully violated, we will transform either the predictor variables or the outcome, depending on the patterning of nonlinearity.

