9.4.2 ANALYSIS OF THE PRIMARY ENDPOINT(S)

Primary Outcomes of Effectiveness Trial - The *multiple* primary outcomes evaluated will be patient-reported measures of illicit opioid use, and mental health functioning. *Opioid use* will be measured using item 7E from the Brief Addiction Monitor (BAM)⁶⁸: “*In the past 30 days, how many days did you use opiates such as Heroin, Morphine, Dilaudid, Demerol, Oxycontin, oxy, codeine (e.g., Tylenol 2,3,4), Percocet, Vicodin, Fentanyl, etc.? Do not count times you used buprenorphine, suboxone, or methadone as directed by a healthcare provider.*” Mental health functioning will be measured using the Mental Component Summary score of the SF-12.

Intent to Treat Analysis of Primary Outcomes of Effectiveness Trial – Given the cluster-randomization we will use appropriate mixed models (also known as multi-level models) to account for clinic effects that are shared by subjects from the same clinic. Measurement occasions (level 1) will be nested within individuals (level 2) which are then nested within clinics (level 3). All outcomes will be analyzed with a multilevel model accounting for clustering of observations (level 1) within patients (level 2) and clinics (level 3). The model will include a random intercept and random linear slope to account for person-level clustering and repeated measures on individual subjects over time that may be associated with variable time trends across participants. To allow for curvilinear change over time, time will be entered as a nominal variable by including dummy codes for the 3- and 6-month time points. The explanatory

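### Baseline differences between arms are to be tested with t-tests and chi-squares that make no allowance for clinic clustering, so the p-values will be too small whenever the clinic ICC is positive

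*Protocol*

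**What the plan says.** Protocol 9.4.4 (Baseline Descriptive Statistics) presents categorical data as percentages and continuous data as means with standard deviations. The plan for testing is that "t-tests and chi-squares will be used to test for group differences at baseline". The reason offered for it is the design, in these words: "Because we are using cluster randomization with a relatively small number of randomization units". The section gives no unit of analysis, clinic-level summary or clinic effect for these tests. Section 9.4.1 sets the level: "An alpha level of 0.05 and two-tailed tests will be used to determine statistical significance".

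Elsewhere the plan does allow for clustering:

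- Protocol 9.4.2, on the primary outcomes: "Given the cluster-randomization we will use appropriate mixed models".
- Protocol 9.2, on power: "a highly conservative intraclass correlation within clinics of 0.03", with 0.01 in the lower-bound scenario.
- SAP 4.1, Equation 1: a random effect for each clinic, applied to all outcomes.

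The SAP neither repeats nor withdraws the baseline tests. Its shell Table S1 shows n (%) or mean (SD) overall and by arm, and has no p-value column.

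**The concern.** The protocol gives cluster randomisation as its reason for testing baseline balance, then names tests whose ordinary form ignores clusters. If patients in the same clinic resemble each other, the variance of a difference between arms exceeds what a plain t-test or chi-square assumes, and chance differences are called significant too often.

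What is at stake is how baseline balance is read. In this trial the question has some content, because clinics are randomised and clinic staff then recruit and consent patients (Protocol 5.4 and 10.1.1.2). Protocol 6.3 masks the survey administrators and 10.1.1.2 withholds the arm from patients, but no masking is described for recruiting staff. A reader could therefore take a significant baseline difference as a sign of differential recruitment. A test with an inflated error rate would raise that suspicion without cause more often than its nominal level implies.

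**Working it through.** **1. The plan's own allowance for clustering.** Protocol 9.2 uses "12 clinics per group and 40 patients per clinic", ICC 0.03 and 80% power, and states that "this power analysis assumes a Bonferroni correction for the two multiple primary outcomes" (0.025 per outcome).

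- Design effect: DE = 1 + (m − 1) × ICC = 1 + 39 × 0.03 = 2.17.
- Standard error of the standardised difference with 480 per arm: √(2 × 2.17 / 480) = 0.0951.
- Detectable effect, noncentral t with 22 df: 0.311, against 0.31 stated (normal approximation 0.293).
- Lower-bound scenario (ICC 0.01, 12 analysed per clinic, DE = 1 + 11 × 0.01 = 1.11): 0.406, against 0.41 stated.

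So the power section does carry a clinic design effect. Section 9.4.4 has no counterpart to it.

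**2. Inputs for the baseline tests.** SAP section 6 gives 254 patients, 28 clinics with at least one patient (mean 254 / 28 = 9.07) and a cluster-size coefficient of variation (CV) of 0.97. No baseline ICC is given. The nearest figures are:

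- the planning values 0.03 and 0.01;
- the SAP's 6-month estimates, adjusted for baseline: 0.00 (SE 0.02) for opioid use and 0.03 (SE 0.09) for the mental component score (MCS).

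The ICC range below is therefore assumed. The value 0.05 is not in the documents, and 0.12 is the MCS estimate plus one SE (0.03 + 0.09).

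**3. Formulas.**

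- DE = 1 + [(1 + CV²) × m − 1] × ICC = 1 + (1.9409 × 9.07 − 1) × ICC = 1 + 16.6 × ICC.
- True two-sided error of an unadjusted 5% test = 2 × [1 − Φ(1.96 / √DE)].

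**4. Results at the achieved size.** The simulation used 28 clinics, 14 per arm, gamma-distributed cluster sizes with CV 0.97, no stratification and 8,000 runs.

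| Assumed ICC | DE | Error, formula | Simulated t-test | Simulated chi-square |
|---|---|---|---|---|
| 0 | 1.00 | 0.050 | 0.049 | 0.050 |
| 0.01 | 1.17 | 0.070 | 0.066 | 0.071 |
| 0.03 | 1.50 | 0.109 | 0.101 | 0.106 |
| 0.05 | 1.83 | 0.147 | 0.142 | 0.133 |
| 0.12 | 2.99 | 0.257 | 0.235 | 0.233 |

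In the same simulation a t-test on clinic means kept its level at every ICC (0.043 to 0.049).

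**5. Planned size, for comparison.** With 1,200 patients in 24 clinics (50 each at baseline) and ICC 0.03, DE = 1 + 49 × 0.03 = 2.47 and the error is 0.212. At ICC 0.01, DE = 1.49 and the error is 0.108.

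**6. Stratification.** Clinics were randomised within healthcare organisation, which balances variation between organisations. As an illustration, assume 14 organisations of two clinics each, randomised in pairs. If half of the ICC lies between organisations, the simulated t-test rejects about 9% of the time at ICC 0.03 and 11% at 0.05. If all of it does, the rates are about 7% and 9%. The split is an assumption; the documents do not give it.

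**The case against.** **The unit of analysis is inferred.** Section 9.4.4 does not say that the tests are run on patients, and a t-test on clinic means would be valid. That is true of the wording. But a chi-square beside percentages, with a Table S1 that counts patients, is hard to read any other way. Where the plan means a clinic-level analysis, as in the pre-post screening analysis of Protocol 9.4.3, it says so.

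**The inflation may be small.** At the SAP's opioid-use estimate of 0.00 there is none. The protocol calls 0.03 highly conservative and 0.01 more realistic, and stratification lowers the rates further. All of this stands and belongs in the stated size. It does not make the tests valid at a positive ICC.

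**Nothing downstream depends on the tests.** A reader might infer that false signs of imbalance would lead to extra adjustment, or would undermine the primary comparison. The documents do not support that. Covariates are chosen on theoretical grounds (Protocol 9.4.1 and 9.4.2) and named in advance (SAP 4.1). The primary contrast, beta5, is a difference in change from baseline, so it removes baseline imbalance in the outcome. For outcome variables, beta1 in Equation 1 already gives a baseline contrast from a model with a clinic random effect. Table S1 has no place for p-values, and the SAP (version 5.0, August 2024) is dated after the protocol's title-page date (February 2024). This objection succeeds in limiting the consequence, but the protocol sentence remains in force.

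**Conclusion.** The point holds as a minor one. As written, Protocol 9.4.4 names baseline tests with no allowance for clinics, and on the natural patient-level reading their p-values are too small whenever the clinic ICC is positive. At the achieved size, the true error of a nominal 5% test is about 5% at ICC 0, 7% at 0.01, 11% at 0.03 and 15% at 0.05, and somewhat less once stratification by organisation is taken into account. These figures rest on an assumed ICC range, because no baseline ICC is reported, and on the achieved cluster sizes in the SAP.

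The consequence is limited to reporting and interpreting baseline balance. The primary estimate, its standard error and the covariate set are untouched. Nor do the documents show that selective recruitment took place, or that a significant baseline test would be treated as proof of it; that is only a reading the tests could invite.

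**What to change.** Replace the testing sentence in Protocol 9.4.4 with two statements:

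- Baseline balance will be described by arm in SAP Table S1 without p-values, for example with standardised differences.
- Any baseline test, such as one meant to look for differential recruitment, will use a model with a clinic random effect or clinic-level means. For outcome variables, beta1 in SAP Equation 1 can serve.

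This also brings Protocol 9.4.4 into line with Table S1. If standardised differences are adopted, Table S1 needs one more column. The cost is one protocol sentence and that column, with no new data and no change to the outcome analyses.

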9.4.5 SUB-GROUP ANALYSES

Because there is evidence that CoCM is more effective for women and minorities, we will conduct a moderation analysis (interaction term between sub-group and intervention group) for our primary outcomes.

9.4.6 EXPLORATORY ANALYSES

Exploratory Implementation Outcomes for Pre-Post Sustainability Evaluation– Participating intervention clinics continuing into the sustainability phase will continue to use the CMTS registry, and we will rely on data from CMTS and provider and clinic level surveys to monitor the implementation success metrics (adoption, reach, effectiveness and intervention fidelity). *Reach* will be measured by the number of patients receiving MOUD and evidence-based treatments for MHS. *Adoption* will be measured by the number of primary care providers prescribing MOUD and psychotropics for MHS.

Effectiveness will be measured using measurement-based care data. Implementation *fidelity* will be measured using the CoCM principles fidelity rubric modified for CHAMP. These six implementation outcomes will be measured at the end of the effectiveness trial and again after six months.

Quantitative Analysis for Pre-Post Sustainability Evaluation - These implementation outcomes measured at end of effectiveness trial will be compared to the implementation outcomes measured at the end of the sustainment period (after six months). The small sample size (n=6 clinics from 4 healthcare systems) will not give us sufficient power to detect anything but large effects. However, we will be able to see trends over time and to compare these distal implementation outcomes to those measures obtained during the effectiveness trial.

Qualitative Data Collection and Analysis for Pre-Post Sustainability Evaluation - We will supplement the quantitative data with qualitative data collected from clinic staff. Purposive sampling will be used to identify stakeholders from each of the 6 clinics. All interviews will be conducted via interactive video (Zoom). **Recruitment/Consent** - Eligible stakeholders will be identified by the study lead at each clinic. After a stakeholder has been identified, research staff will recruit them by email and or phone. Stakeholders will be considered study participants. We will mail or email stakeholders the "CHAMP Summative Evaluation Information Sheet". We will obtain an audio-recorded verbal agreement to participate in the qualitative interviews rather than written informed consent because the signed consent form would be the only identifying information collected (thereby increasing the risk of loss of confidentiality). In addition, participation in the qualitative interviews is considered to be no more than minimal risk. **Interview Guide**: The interview guide is organized by type of implementation outcome (sustainment mechanisms of action, proximal, distal), and three types of determinants that can be a barrier or facilitator of implementation success: 1) outer setting, 2) inner setting, and 3) fit between the clinical intervention and the outer and inner settings. A blend of grand-tour and specific probe questions will be used. **Analysis** - Using a typology of mixed method approaches, we will use the qualitative data to provide convergence with the quantitative data. This will include: 1) triangulation across data streams to corroborate findings (focusing on distal outcomes), 2) complementarity to gain additional depth of understanding and focus on process and context (across all outcomes), and 3) development of a conceptual model used to generate hypotheses. Two qualitative data analytic approaches will be used. A directed content analytic approach will be used to assess the distal implementation outcomes. This approach blends deductive and inductive analysis and will be used to provide depth and context to site level performance data on reach, adoption, and fidelity. A more grounded thematic analysis approach will be used to examine the potential impacts of the sustainment strategies on the proposed mechanisms of action and proximal outcomes. This approach will be largely inductive and focused on developing an initial model of mechanisms of action.

10 SUPPORTING DOCUMENTATION AND OPERATIONAL CONSIDERATIONS

10.1 REGULATORY, ETHICAL, AND STUDY OVERSIGHT CONSIDERATIONS

10.1.1 INFORMED CONSENT PROCESS

10.1.1.1 CONSENT/ASSENT AND OTHER INFORMATIONAL DOCUMENTS PROVIDED TO PARTICIPANTS

Consent forms describing in detail the study intervention, study procedures, and risks will be given to the participant and written documentation of informed consent will be completed prior to starting the study intervention. The consent form is included with this protocol.

10.1.1.2 CONSENT PROCEDURES AND DOCUMENTATION

After a patient has been determined to be eligible (see eligibility workflow in section 5), clinic staff will recruit and consent the patient. Clinics will maintain electronic or hardcopies of the original consent form. Patients will be given an electronic or hardcopy of the signed consent form. Staff will not sign the consent form as a witness to the signature. Clinics may consent patients in one of two ways: in-person consenting or virtual e-consenting.

1. In-person consenting: clinic staff will provide information about the study to the patient in person using a REDCap e-consent form or a hardcopy of the informed consent form. Clinic staff will facilitate patient comprehension by providing opportunity for patient to consider the information and ask questions. Clinic staff will document consent using a REDCap e-consent form on a tablet or a hardcopy of the informed consent form. The signed REDCap e-consent form will automatically save a PDF of the electronic consent form that is immediately accessible to the UW study team to verify that the patient has enrolled in the study. A scanned PDF of the signed hardcopy consent form will be sent to UW to verify that the patient has enrolled in the study and to ensure that signatures are valid and dates are present.
2. Virtual e-consenting: clinic staff will provide information about the study to the patient virtually by tele-video or audio-only telephone. Clinic staff will facilitate patient comprehension by providing opportunity for patients to consider the information and ask questions. Clinic staff will document consent using a REDCap e-consent form or a hardcopy of the informed consent form. The REDCap e-consent form will be emailed to the patient to sign on their phone or computer. The hardcopy informed consent form can be mailed to the patient and returned if email is not available to the patient. The signed REDCap e-consent form will automatically save a PDF of the electronic consent form that is immediately accessible to the UW study team to verify that the patient has enrolled in the study. A scanned PDF of the signed hardcopy consent form will be sent to UW to verify that the patient has enrolled in the study and to ensure that signatures are valid and dates are present.

The modified⁷⁶ informed consent process will disclose the general purpose of the study, the evaluation data collection research activities, the risks of participating in the data collection activities, the protection against those risks, and the alternatives to participating, but patients will not be told which study arm their clinic has been randomized to.⁷⁷ We chose to not disclose this information to support the internal and external validity of the Effectiveness trial.

Consent forms will be available both in English and in Spanish.

10.1.2 STUDY DISCONTINUATION AND CLOSURE

This study may be temporarily suspended or prematurely terminated if there is sufficient reasonable cause. Written notification, documenting the reason for study suspension or termination, will be provided by the suspending or terminating party to the study participants, funding agency, and

regulatory authorities. If the study is prematurely terminated or suspended, the Principal Investigator (PI) will promptly inform study participants, the Institutional Review Board (IRB), and sponsor/funding agency and will provide the reason(s) for the termination or suspension. Study participants will be contacted, as applicable, and be informed of changes to study visit schedule.

Circumstances that may warrant termination or suspension include, but are not limited to:

- Determination of unexpected, significant, or unacceptable risk to participants
- Demonstration of efficacy that would warrant stopping
- Insufficient compliance to protocol requirements
- Data that are not sufficiently complete and/or evaluable
- Determination of futility

10.1.3 CONFIDENTIALITY AND PRIVACY

[figure not shown]
Participant confidentiality and privacy is strictly held in trust by the participating investigators, their staff, the safety and oversight monitor(s), and funding agency. This confidentiality is extended to the data being collected as part of this study. Data that could be used to identify a specific study participant will be held in strict confidence within the research team. No personally-identifiable information from the study will be released to any unauthorized third party.

The data files with eligibility criteria, survey response and information extracted from CMTS will not contain any identifying information about study participants, but will contain a unique study ID. We will maintain a separate file that contains the study ID and participant's identifying information. This separate file containing participant's identifying information will only be available to the study team, and organizations that make sure studies like this are done safely. Specifically, the Institutional Review Board, the National Institutes of Health, and the Federal Office for Human Research Protections will be able to inspect and copy confidential study-related records which identify study participants' by name. This is to make sure the research team is conducting the Effectiveness trial safely and legally.

Certificate of Confidentiality – This research is covered by a Certificate of Confidentiality from the National Institutes of Health. The researchers with this Certificate may not disclose or use information, or documents that may identify study participants in any federal, state, or local civil, criminal, administrative, legislative, or other action, suit, or proceeding, or be used as evidence, for example, if there is a court subpoena, unless a study participant has consented for this use. Information, or documents protected by this Certificate cannot be disclosed to anyone else who is not connected with the research except, if there is a federal, state, or local law that requires disclosure or if a study participant has consented to the disclosure, or if it is used for other scientific research, as allowed by federal regulations protecting research subjects. The Certificate cannot be used to refuse a request for information from personnel of the United States federal or state government agency sponsoring the project that is needed for auditing or program evaluation by the agency which is funding this project or for information that must be disclosed in order to meet the requirements of the federal Food and Drug Administration (FDA). The Certificate of Confidentiality will not be used to prevent disclosure as required by federal, state, or local law of, for instance, child abuse or neglect, harm to self or others, and communicable diseases. If we learn that study participants intend to harm others, we will report that to the authorities. Also, if a study participant reports that they intend to harm themselves, we will connect them with professionals trained in suicide prevention and notify their primary care team.

